#### 4.5.19.1 Local Laboratory Assessments

Samples for the following laboratory tests will be sent to the study site's local laboratory for analysis:

- Urinalysis: A urine dipstick for blood, protein, nitrite, and glucose (using the dipsticks provided) will be performed according to the schedule of activities (see Appendix 1). If abnormal and applicable, a microscopic examination will be performed on site (local laboratory).
- Pregnancy test: Urine pregnancy test (sensitivity of at least 25 mIU/mL β–hCG) for all females of childbearing potential (Tanner Stage 2 or above or onset of menarche during the study)

On infusion visits, the urine samples for the urinalysis and pregnancy test should be performed prior to the methylprednisolone infusion and the ocrelizumab dose withheld for a positive pregnancy test result.

A positive urine pregnancy test should be confirmed with a serum test through the central laboratory prior to any further dosing with ocrelizumab.

## 4.5.19.2 Central Laboratory Assessments

In order to ensure patient safety in the study and to allow for assessments of the retreatment criteria, a central laboratory will provide study investigators and Medical Monitors with reflex messages triggered by critical laboratory results.

The reflex messages from a central laboratory, together with laboratory results, should be carefully reviewed at every visit before continuing with ocrelizumab treatment.

Investigators notified of a patient's critical laboratory test results will be instructed to suspend further treatment with study drug until the patient becomes eligible for re-treatment (see Section 4.3.6).

The reflex messages will be in effect during the entire study duration. Further details will be provided in the Laboratory Manual.

- Hematology: WBC count (absolute and differential), RBC count, RBC morphology, hemoglobin, hematocrit, quantitative platelet count, and ANC count
- Blood chemistry: AST, ALT, gamma glutamyl transferase, alkaline phosphatase, amylase, lipase, total protein, albumin, cholesterol, total bilirubin (direct and indirect will be performed if total bilirubin is greater than the ULN), uric acid, potassium, sodium, chloride, calcium, phosphorus, LDH, CPK, and triglycerides

# Ocrelizumab—F. Hoffmann-La Roche Ltd

78/Protocol WA39085, Version 10

- Thyroid function test: Sensitive thyroid-stimulating hormone (TSH) will be tested as outlined in the schedule of activities (see Appendix 1). Thyroid autoantibodies (i.e., thyroid peroxidase antibody, thyroglobulin antibody) will be assayed only at screening.
- Immunologic assessments: Determination of B– and T–cell populations and natural killer cells
- Quantitative Ig levels: Including total Ig, IgG, IgM, and IgA isotypes
- Antibody titers: Measurement of antibody titers to common antigens (mumps, rubella, varicella, *S. pneumoniae*) will be performed.
- ADA: Serum samples will be collected for determination of antibodies against ocrelizumab. Because ocrelizumab concentrations affect the ADA assay, the concentration of ocrelizumab will be measured as well at all timepoints with ADA assessment to enable interpretation of the results (PK sample).

On infusions visits, all samples must be taken prior to the methylprednisolone infusion.

For more information, refer to the schedule of activities (see Appendix 1).

## 4.5.19.3 Laboratory Tests Performed at Screening

The following laboratory tests will be performed at screening:

- Pregnancy test: A serum pregnancy test will be performed at screening for all females of childbearing potential and will be sent for central laboratory analysis.
- Hepatitis serology: HBcAb, HBsAg, and HepCAb at screening only or if clinically indicated during the trial
- Thyroid function test: sensitive TSH and thyroid autoantibodies (i.e., thyroid peroxidase antibody, thyroglobulin antibody) at screening
- Rapid plasma regain

See also Section 4.1.2.3 (Exclusions Related to Laboratory Findings).

## 4.5.19.4 Hepatitis Screening and Liver Function Monitoring

Patients with recurrent or chronic hepatitis B or history/presence of hepatitis C infection must be excluded from enrollment into the study. Hepatitis B and C serology will be performed at screening.

A positive result to either HBsAg, total HBcAb associated with positive viral DNA titers as measured by PCR, or a positive result for HepCAb should result in the patient's exclusion.

Patients with evidence of past resolved hepatitis B infection (i.e., positive total HBcAb associated with a negative viral DNA) can be enrolled and will have the hepatitis B viral DNA checked regularly as per the schedule of activities (see Appendix 1).

#### **Ocrelizumab—F. Hoffmann-La Roche Ltd** 79/Protocol WA39085, Version 10

Patients in whom the viral DNA becomes positive but in whom the quantity is at the lower limit of detection of the assay should have the test repeated as soon as possible. Patients found to have a confirmed viral DNA–positive test should be referred to a hepatologist for immediate assessment. These patients will not receive further ocrelizumab infusions and will enter the SFU period.

Liver function (i.e., ALT, AST, gamma glutamyl transferase, alkaline phosphatase, and total bilirubin) should be reviewed throughout the study. Patients developing evidence of liver dysfunction should be assessed for viral hepatitis and, if necessary, referred to a hepatologist or other appropriately qualified expert. Study drug should be withheld until the diagnosis of viral hepatitis has been excluded.

Patients developing hepatitis B or C should be withdrawn from the study and should enter the SFU period. Should treatment be prescribed, this will be recorded on the eCRF. Patients with viral hepatitis due to other agents, such as hepatitis A, may resume treatment after the patient's recovery.

# 4.5.19.5 Plasma and Urine Banking for JC–virus

Long-term storage of plasma samples and urine is planned for JC–virus (JCV) DNA and/or other relevant tests for JCV, independent of an occurrence of suspected PML case (see Section 5.1.2.2). Plasma samples (5 mL) and urine samples (10 mL) will be collected as per the schedule of activities (see Appendix 1). As there have been no cases of PML reported with ocrelizumab and a correlation between viremia and onset of PML has not been established for another anti-CD20 therapy, JCV samples will not be used to determine study participation or treatment decisions. The JCV assessments in plasma and urine will be performed if deemed necessary in the future and not on an ongoing basis.

# 4.5.19.6 Pharmacokinetic/Pharmacodynamic Assessments Pharmacokinetics

First ocrelizumab dose (Dose 1, Days 1 and 15):

PK samples (2 mL blood for serum) will be collected on the infusion day at Days 1 and 15 at 5–30 minutes before the methylprednisolone infusion and 30 ( $\pm$ 10) minutes after the completion of the ocrelizumab infusion.

In addition, during the 24–week dose exploration period, one PK sample each will be collected any time during visits at Weeks 4, 8, 12, 16, and 24 (prior to the next infusion of ocrelizumab for patients continuing in the OOE period).

#### Subsequent ocrelizumab doses in the OOE period:

A PK sample will also be collected predose before each infusion during the OOE period, until Week 96, at a withdrawal from treatment visit, and during the SFU period as outlined in the schedule of activities (see Appendix 1).

Note: The PK sample must be collected from the arm opposite the arm receiving the IV infusion of ocrelizumab.

## Pharmacodynamics

CD19 B–cell count in blood will be performed at baseline; Weeks 2, 4, 8, 12, 16, and 24; and at further timepoints as outlined in the schedule of activities (see Appendix 1).

# 4.5.19.7 Blood Samples for Biomarker Research

Serum samples will be collected for exploratory research on biomarkers.

These samples will be collected according to the schedule of activities (see Appendix 1) and analysis will include, but may not be limited to neurofilament light chain. Biomarker samples will be sent to one or several central laboratories or to the Sponsor or a designee. Samples may be processed by the Sponsor's laboratory or the Sponsor's qualified designated laboratory (Contract Research Organization and/or academic research laboratory affiliated with the study). Instructions for the collection and handling of biomarker samples, including sampling procedures, storage conditions, and shipment instructions, are provided in the laboratory manual.

Unless the patient and/or their parent(s)/legal guardian(s) gives specific consent for the patient's leftover samples to be stored for optional exploratory research (see Section 4.5.20), biomarker samples will be destroyed no later than 5 years after the final Clinical Study Report has been completed.

When a patient withdraws from the study, samples collected prior to the date of withdrawal may still be analyzed, unless the patient and/or their parent(s)/legal guardian(s) specifically requests that the samples be destroyed, or local laws require destruction of the samples. However, if samples have been tested prior to withdrawal, results from those tests will remain as part of the overall research data.

Data arising from sample analysis will be subject to the confidentiality standards described in Section 8.4.

Given the complexity and exploratory nature of exploratory biomarker analyses, data derived from these analyses will generally not be provided to investigators, patient and/or their parent(s)/legal guardian(s) unless required by law. The aggregate results of any conducted research will be available in accordance with the effective Sponsor policy on study data publication.

# 4.5.20 Optional Samples for Research Biosample Repository 4.5.20.1 Overview of the Research Biosample Repository

The Research Biosample Repository (RBR) is a centrally administered group of facilities used for the long-term storage of human biological specimens, including body fluids, solid tissues, and derivatives thereof (e.g., DNA, RNA, proteins, peptides). The

collection, storage, and analysis of RBR samples will facilitate the rational design of new pharmaceutical agents and the development of diagnostic tests, which may allow for individualized drug therapy for patients in the future.

Samples for the RBR will be collected from patients who give specific consent or who have been given specific consent by their parent(s)/legal guardian(s) to participate in this optional research. RBR samples will be analyzed to achieve one or more of the following objectives:

- To study the association of biomarkers with efficacy or disease progression
- To identify safety biomarkers that are associated with susceptibility to developing adverse events or can lead to improved adverse event monitoring or investigation
- To increase knowledge and understanding of disease biology and drug safety
- To study drug response, including drug effects and the processes of drug absorption and disposition
- To develop biomarker or diagnostic assays and establish the performance characteristics of these assays

#### 4.5.20.2 Approval by the Institutional Review Board or Ethics Committee

Collection, storage, and analysis of RBR samples is contingent upon the review and approval of the exploratory research and the RBR portion of the Informed Consent Form by each site's IRB/EC and, if applicable, an appropriate regulatory body. If a site has not been granted approval for RBR sampling, this section of the protocol (Section 4.5.20) will not be applicable at that site.

# 4.5.20.3 Sample Collection

The following samples will be stored in the RBR and used for research purposes, including, but not limited to, research on biomarkers related to ocrelizumab, diseases, or drug safety:

- Optional blood collection for DNA
- Leftover blood, serum and plasma

The above samples may be sent to one or more laboratories for analysis of germline or somatic variants via whole-genome sequencing (WGS), whole-exome sequencing (WES), or other genomic analysis methods. Genomics is increasingly informing researcher's understanding of disease pathobiology. WGS and WES provide a comprehensive characterization of the genome and exome, respectively, and, along with clinical data collected in this study, may increase the opportunity for developing new therapeutic approaches or new methods for monitoring efficacy and safety or predicting which patients are more likely to respond to a drug or develop adverse events.

Data generated from RBR samples will be analyzed in the context of this study but may also be explored in aggregate with data from other studies. The availability of a larger

Ocrelizumab—F. Hoffmann-La Roche Ltd 82/Protocol WA39085, Version 10 dataset will assist in identification and characterization of important biomarkers and pathways to support future drug development.

For sampling procedures, storage conditions, and shipment instructions, see the laboratory manual.

RBR samples are to be stored until they are no longer needed or until they are exhausted. However, the RBR storage period will be in accordance with the IRB/EC–approved Informed Consent Form and applicable laws (e.g., health authority requirements).

# 4.5.20.4 Data Protection, Use, and Sharing

RBR samples and associated data will be labeled with a unique patient identification number.

Patient medical information associated with RBR samples is confidential and may be disclosed to third parties only as permitted by the Informed Consent Form (or separate authorization for use and disclosure of personal health information) signed by the patient and/or their parent(s)/legal guardian(s), unless permitted or required by law.

Data generated from RBR samples will be analyzed in aggregate rather than on an individual patient basis. Thus, there will be no identification and reporting of incidental findings to investigators or patients and/or their parent(s)/legal guardian(s). In addition, given the complexity and exploratory nature of the analyses of RBR samples, data derived from these analyses will generally not be provided to study investigators or patient and/or their parent(s)/legal guardian(s), unless required by law, with the exception of data generated from blood samples collected for WGS or WES as described below.

If permitted by local law, a patient and/or their parent(s)/legal guardian(s) may request access to uninterpreted WGS or WES data derived from analysis of the patient's blood sample. If a patient and/or their parent(s)/legal guardian(s) wishes to access these data, the investigator must inform the Sponsor, using the following email address:

#### [contact]

The Sponsor will provide available data to the investigator in the form of a raw genomic sequencing data file, but will not provide any interpretation of the data. The investigator should not include the data file in the patient's medical record. Samples may be stored and analyzed in the future, and some samples may never be analyzed. Thus, data may not be available at the time of the request or may never be available.

The aggregate results of any conducted research will be available in accordance with the effective Sponsor policy on study data publication.

Data generated from RBR samples must be available for inspection upon request by representatives of national and local health authorities, and Sponsor monitors, representatives, and collaborators, as appropriate.

Any inventions and resulting patents, improvements, and/or know-how originating from the use of the RBR data will become and remain the exclusive and unburdened property of the Sponsor, except where agreed otherwise.

# 4.5.20.5 Consent to Participate in the Research Biosample Repository

The Informed Consent Form will contain a separate section that addresses participation in the RBR. The investigator or authorized designee will explain to each patient and/or their parent(s)/legal guardian(s) the objectives, methods, and potential hazards of participation in the RBR. Patients and/or their parent(s)/legal guardian(s) will be told that they are free to choose not to provide optional RBR samples and may withdraw their consent at any time and for any reason during the storage period. A separate, specific signature from the patient and/or their parent(s)/legal guardian(s) will be required to document a patient's agreement to provide optional RBR samples. Patients and/or their parent(s)/legal guardian(s) who choose not to provide optional RBR samples will not provide a separate signature. The investigator should document whether or not the patient and/or their parent(s)/legal guardian(s) has given consent to provide optional RBR samples and (if applicable) the date of consent, by completing the Sample Informed Consent/Withdrawal eCRF.

In the event of an RBR patient's death or loss of competence, the patient's samples and data will continue to be used as part of the RBR research.

# 4.5.20.6 Withdrawal from the Research Biosample Repository

Patients and/or their parent(s)/legal guardian(s) who give consent to provide RBR samples have the right to withdraw their consent at any time for any reason. After withdrawal of consent, any remaining samples will be destroyed. However, if RBR samples have been tested prior to withdrawal of consent, results from those tests will remain as part of the overall research data. If a patient and/or their parent(s)/legal guardian(s) wishes to withdraw consent to the testing of the patient's RBR samples during the study, the investigator must inform the Medical Monitor in writing of the patient and/or their parent(s)/legal guardian(s)'s wishes through use of the appropriate RBR Subject Withdrawal Form and must enter the date of withdrawal on the Sample Informed Consent/Withdrawal eCRF. If a patient and/or their parent(s)/legal guardian(s) wishes to withdraw consent to the testing of the patient (s)/legal guardian(s) wishes to withdrawal eCRF. If a patient and/or their parent(s)/legal guardian(s) wishes to withdraw consent to the testing of the patient (s)/legal guardian(s) wishes to withdrawal eCRF. If a patient and/or their parent(s)/legal guardian(s) wishes to withdraw consent to the testing of the patient's RBR samples after closure of the site, the investigator must inform the Sponsor by emailing the study number and participant number to the following email address:

[contact]

A patient and/or their parent(s)/legal guardian(s)'s withdrawal from this study does not, by itself, constitute withdrawal of consent for testing of RBR samples. Likewise, a

Ocrelizumab—F. Hoffmann-La Roche Ltd 84/Protocol WA39085, Version 10 patient and/or their parent(s)/legal guardian(s)'s withdrawal of consent for testing of RBR samples does not constitute withdrawal from this study.

# 4.5.20.7 Monitoring and Oversight

RBR samples will be tracked in a manner consistent with Good Clinical Practice by a quality-controlled, auditable, and appropriately validated laboratory information management system, to ensure compliance with data confidentiality as well as adherence to authorized use of samples as specified in this protocol and in the Informed Consent Form. Sponsor monitors and auditors will have direct access to appropriate parts of records relating to an individual's participation in the RBR for the purposes of verifying the data provided to the Sponsor. The site will permit monitoring, audits, IRB/EC review, and health authority inspections by providing direct access to source data and documents related to the RBR samples.

# 4.6 TREATMENT, PATIENT, STUDY, AND SITE DISCONTINUATION

# 4.6.1 Study Treatment Discontinuation

Patients must permanently discontinue study treatment if they experience any of the following:

- Any medical condition that the investigator or Sponsor determines may jeopardize the patient's safety if he or she continues to receive study treatment
- Investigator or Sponsor determines it is in the best interest of the patient
- Life-threatening (Grade 4) infusion-related event or severe allergic or anaphylactic reaction to an ocrelizumab infusion
- Active hepatitis B or C infection, either new onset or reactivation in the case of hepatitis B
- PML
- Treatment emergent life-threatening (Grade 4) infection

It is important to distinguish between "withdrawal from treatment" and "withdrawal from study." Patients who withdraw from treatment should be encouraged to remain in the study for the full duration of the SFU period (104 weeks following the last infusion).

A complete final evaluation at the time of the patient's withdrawal should be made with an explanation of why the patient is withdrawing from the study.

If the parents/legal guardians or patients insist on withdrawing (their child) from the study, he/she will not be followed for any reason after consent and/or assent withdrawal. The outcome of that discussion should be documented in both the medical records and on the eCRF. If lost to follow-up, the investigator should contact the parents/legal guardians/patient or a responsible relative by telephone followed by registered mail or through a personal visit to establish as completely as possible the reason for the withdrawal.

#### Ocrelizumab—F. Hoffmann-La Roche Ltd 85/Protocol WA39085, Version 10

It should be noted that upon withdrawal from the study, any untested routine samples will be destroyed. However, information already obtained from samples up until the time of withdrawal will not be destroyed.

An excessive rate of withdrawals can render the study non-interpretable; therefore, unnecessary withdrawal of patients should be avoided. Should a patient decide to withdraw, all efforts will be made to complete and report the observations prior to withdrawal as thoroughly as possible.

The primary reason for study treatment discontinuation should be documented on the appropriate eCRF. Patients who discontinue study treatment will not be replaced.

## 4.6.2 Patient Discontinuation from Study

Patients who discontinue study participation and withdraw consent or assent, as applicable, will not be required to return for any follow-up assessments.

Parents/legal guardians have the right to withdraw their child from the study at any time for any reason.

Patients have the right to voluntarily withdraw from the study at any time for any reason. In addition, the investigator has the right to withdraw a patient from the study at any time. Reasons for withdrawal from the study may include, but are not limited to, the following:

- Patient withdrawal of consent or assent, as applicable
- Parents/legal guardian withdrawal of consent
- Study termination or site closure
- Investigator or Sponsor determines it is in the best interest of the patient

When applicable, parents/guardians/patients should be informed of circumstances under which their (child's) participation may be terminated by the investigator without parent/guardian/patient consent. The investigator may withdraw patients from the study in the event of intercurrent illness, adverse events, treatment failure, after a prescribed procedure, lack of compliance with the study and/or study procedures (e.g., dosing instructions, study visits), or any reason where it is believed by the investigator that it is in the best interest of the patient to be terminated from the study. Any administrative or other reasons for withdrawal must be documented and explained to the patient. If the reason for removal of a patient from the study is an adverse event, the principal specific event will be recorded on the eCRF. If possible, the patient should be followed until the adverse event has resolved.

Every effort should be made to obtain information on patients who withdraw from the study as thoroughly as possible. The primary reason for withdrawal from the study should be documented on the appropriate eCRF. However, patients will not be followed for any reason after consent has been withdrawn. Patients who withdraw from the study

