# 3.1.1.4 *104*-Week Safety Follow-Up Period (Including B-Cell Monitoring Period, if Required)

Patients completing the 288–week treatment period or patients who discontinue treatment prematurely for any reason at any time during the study will enter the SFU period.

The SFU period will last for at least 104 weeks starting from the date of the last infusion of ocrelizumab. However, patients whose peripheral blood B cells remain depleted will continue to be monitored until their B–cell counts have returned to baseline level or to the LLN range (whichever is lower) (see Figure 2).

The decision to initiate an alternative treatment for MS during this SFU period will be at the discretion of the treating investigator.

A dedicated SFU visit (scheduled or unscheduled) directly prior to the start of an alternative MS treatment is required in order to assess the patient's clinical status and safety. Information about the alternative treatment, such as dose, route, and frequency, will be recorded on the electronic case report form (eCRF).

Patients who receive MS therapies that may change B-cell levels during the SFU period will not be entered into the prolonged B-cell monitoring period thereafter.

Because sufficient data are not available to inform risks associated with switching to other products, caution is advised while patients remain B cell depleted.

Because of the unknown safety risk of administering DMTs for MS after discontinuation of ocrelizumab, certain treatments for MS such as lymphocyte–depleting agents or lymphocyte–trafficking blockers (e.g., alemtuzumab, natalizumab, fingolimod, dimethyl fumarate, cyclophosphamide, azathioprine) are strongly discouraged for as long as the patient remains B cell depleted on account of unknown effects on the immune system (e.g., increased risk, incidence, or severity of infection).

SFU visits will be performed at 12–week intervals starting from the date of the patient's last visit (e.g., withdrawal from treatment visit or Week 288 visit). For sites where mobile nursing (MN) is used, SFU visits can alternate between site visits and MN visits for the patient's convenience.

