# 4.5.3.6 Withdrawal Visit

At the moment a patient meets one or more of the withdrawal criteria, or if a patient does not want to continue in the OOE period, this patient is regarded as withdrawn from treatment. Patients who withdraw from ocrelizumab treatment must complete all assessments (i.e., withdrawal visit) as shown in the schedule of activities (see Appendix 1) and will enter the SFU period.

It is important to distinguish between "withdrawal from treatment" and "withdrawal from study." Patients who withdraw from treatment should be encouraged to remain in the study for the full duration of the SFU period (104 weeks following the last infusion).

Despite all efforts, patients who withdraw from the study before entering the SFU period or during the SFU period should undergo the assessments shown in the schedule of activities.

At the withdrawal visit, an MRI scan will be required only if one was not performed in the previous 4 weeks. Thereafter, it is at the discretion of the treating investigator to decide on further treatment of the underlying disease. However, since sufficient data are not available to inform risks associated with switching to other products, the following recommendations are given:

- Caution is advised while patients remain B-cell depleted.
- Because of the unknown safety risk of administering DMTs for MS after discontinuation of ocrelizumab, certain treatments for MS such as lymphocytedepleting agents or lymphocyte-trafficking blockers (e.g., alemtuzumab, natalizumab, fingolimod, dimethyl fumarate, cyclophosphamide, azathioprine) are strongly discouraged for as long as the patient remains B cell depleted because of unknown effects on the immune system (e.g., increased risk, incidence, or severity of infection).

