#### 6.6 SAFETY ANALYSES

Safety data will be listed individually and summarized descriptively by cohort/dose level for the Dose Exploration period and the OOE. The exposure period (time at risk) for each safety endpoint is defined as time from the date of the first exposure to the study treatment to the date of study withdrawal or clinical cutoff date, whichever occurs earlier.

The safety endpoints include, but may not be limited to, the following:

- Incidence of adverse events (overall, by severity, and by relationship to study medication)
- Incidence of serious adverse events
- Incidence of treatment discontinuations due to adverse events
- Change from baseline by time in laboratory parameters and incidence of clinically significant laboratory abnormalities
- Change from baseline by time in vital signs (systolic blood pressure, diastolic blood pressure, pulse rate, respiratory rate, body temperature) and incidence of vital sign abnormalities

The incidence count for each adverse event will be defined as the number of patients reporting at least one treatment-emergent occurrence of the event. The incidence rate will be calculated as the incidence count divided by the total number of patients in each cohort as well as total. In addition, the rate per 100 patient-years (along with the 95% confidence interval using the exact method based on the Poisson distribution) will be calculated for all adverse events and serious adverse events.

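### Section 4.6.2 lets the investigator take a child out of the study for an adverse event or treatment failure, which conflicts with the rule that treatment stoppers enter at least 104 weeks of safety follow-up, so follow-up may be cut short for outcome-related reasons

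*Combined protocol and SAP*

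**What the plan says.** **Rules that keep the child under observation.** Section 3.1.1.4 states that "patients who discontinue treatment prematurely for any reason at any time during the study will enter the SFU period", and that "The SFU period will last for at least 104 weeks starting from the date of the last infusion of ocrelizumab". Section 3.4.6 extends this to every patient given at least one dose. Sections 4.5.3.6 and 4.6.1 both open the matter with "It is important to distinguish between", then contrast withdrawal from treatment with withdrawal from study and encourage treatment stoppers to stay for the whole SFU.

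**The rule that can end observation.** Section 4.6.2 provides: "The investigator may withdraw patients from the study in the event of intercurrent illness, adverse events, treatment failure". It goes on to list non-compliance and any other best-interest reason. It says families should be told when "participation may be terminated by the investigator without parent/guardian/patient consent". For a child removed because of an adverse event it asks only: "If possible, the patient should be followed until the adverse event has resolved".

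**The pointer.** Section 4.3.2 tells sites that guidance on interrupting or stopping treatment after an adverse event is in 4.6.2. The list of treatment stops is in 4.6.1.

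**Hepatitis.** Section 4.5.19.4 reads: "Patients developing hepatitis B or C should be withdrawn from the study and should enter the SFU period". Section 4.6.1 lists active hepatitis B or C as a reason to stop study treatment.

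**The analysis.** Section 6.6 runs time at risk from first exposure "to the date of study withdrawal or clinical cutoff date, whichever occurs earlier".

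**The concern.** The protocol handles an adverse event in two ways. Under 3.1.1.4 the child stops treatment and stays under scheduled observation. Under 4.6.2 the same event is a ground for leaving the study, and nothing there mentions the SFU. The best-interest criterion has the same problem: it appears both as a treatment stop in 4.6.1 and as a study withdrawal in 4.6.2.

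If a site takes the second route, the end of observation depends on the outcome being studied. What would be missing is the later course in a child who had a safety problem: laboratory values, immunoglobulins, B-cell repletion, MRI and EDSS from Appendix 1, Table 3. In adults the median time to B-cell repletion was 72 weeks, range 27 to 175 (Section 1.2.2), so early removal can lose the repletion data that 3.4.6 gives as a purpose of the SFU. Section 4.6.1 adds that untested routine samples are destroyed once a patient withdraws from the study.

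**Working it through.** **Stated figure.** Section 3.3 gives about 402 weeks of participation. Maximum screening 10 + dose exploration 24 + extension 264 + SFU 104 = 402. It reproduces, and it includes the full 104 weeks. With the standard 8-week screening the sum is 400.

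**No power calculation applies.** Section 6 is descriptive only, and 6.1 sets 6 patients per dose cohort for feasibility. The effect is therefore expressed as lost observation.

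**Loss per child.** If removal coincides with the last infusion, the whole SFU minimum is lost: 104 / 52.18 = 1.99, about 2.0 patient-years. This is a ceiling on the 104-week minimum. Removal 24 weeks after the last infusion would lose 104 − 24 = 80 weeks.

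**Share of planned post-treatment observation, cohort of 6.** One child: 104 / (6 × 104) = 17%. Two children: 33%. Cohort 2 has at least 6 patients, so its share can be smaller.

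**Share of total time at risk, cohort of 6.** Assumptions: the other children contribute F = 368 weeks (264 + 104, counting the SFU from the last scheduled infusion) or 392 weeks (288 + 104, counting it from Week 288). The removed child leaves at week t = 24 or 96, with the last infusion taken to be at that time. With m children removed:

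- kept in SFU: (6 − m) × F + m × (t + 104) weeks
- removed: (6 − m) × F + m × t weeks

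| m | F | t | Kept (patient-years) | Removed (patient-years) | Loss |
|---|---|---|---|---|---|
| 1 | 368 | 24 | 37.7 | 35.7 | 5.3% |
| 1 | 392 | 96 | 41.4 | 39.4 | 4.8% |
| 2 | 368 | 24 | 33.1 | 29.1 | 12.0% |
| 2 | 392 | 96 | 37.7 | 33.7 | 10.6% |

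Example, third row: kept (4 × 368 + 2 × 128) / 52.18 = 1728 / 52.18 = 33.1; removed (4 × 368 + 2 × 24) / 52.18 = 1520 / 52.18 = 29.1; loss 208 / 1728 = 12.0%.

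**Effect on a rate.** Take the exact Poisson interval named in 6.6, with an assumed k = 3 events and T patient-years. The lower limit is χ²(0.025; 2k) / (2T) and the upper limit is χ²(0.975; 2k + 2) / (2T), each times 100. For the third row the rate moves from 9.1 (95% CI 1.9 to 26.5) to 10.3 (2.1 to 30.1) per 100 patient-years. Events are held at 3, so this shows the denominator effect only. Any events in the lost time would also go unseen.

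**Hepatitis.** Section 4.5.19.4 orders entry to the SFU in the same sentence, so the loss as written is 0 weeks. The difficulty is one of recording: if study withdrawal is entered literally, 6.6 stops the clock while the child is still attending SFU visits.

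**The case against.** The strongest reply is that the two sections govern different acts: 3.1.1.4 covers stopping treatment, 4.6.2 covers leaving the study, and the protocol itself insists on the difference. The 4.6.2 clause is permissive, and 4.6.1 says unnecessary withdrawals should be avoided. Grade 4 infusion reactions (4.3.4.2) and Grade 4 infections (4.3.6) lead explicitly to the SFU, and confirmed PML (4.5.15) is a withdrawal from treatment.

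There are also safeguards. Section 4.5.3.6 asks for assessments at study withdrawal. Section 5.5.1 follows each known event to resolution or stability. Section 4.6.2 asks for every effort to obtain information. Section 5.6 keeps deaths and known drug-related serious events reportable.

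Much of this stands. It shows that loss of follow-up is possible, not prescribed, and that the known event would usually be followed. It does not remove the conflict. The same event is listed as a ground for study withdrawal, and 4.3.2 points sites there. Nor do the safeguards replace scheduled visits, which exist to find what is not yet known.

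A reader might go further and infer any of three things that the documents do not support:

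- That hepatitis patients lose follow-up. Section 4.5.19.4 sends them to the SFU.
- That follow-up is in fact cut short in children who are harmed. The clause is discretionary, and no count of removals is given.
- That the SFU was lengthened to capture exactly these data. The Version 10 rationale cites FDA postmarketing requirements without saying which data were wanted.

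Ending time at risk at study withdrawal is not in itself an error. It becomes a problem only when withdrawal can be triggered by the outcome.

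**Conclusion.** The concern holds as a conflict that may shorten safety follow-up informatively. Sections 4.6.2 and 4.3.2 do not agree with 3.1.1.4, 3.4.6 and 4.6.1 on what happens to a child with an adverse event or treatment failure, and 6.6 carries the consequence into the safety rates.

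The upper bound is 104 weeks per child, or 17% of planned post-treatment observation for one child in a cohort of 6. It assumes removal at the last infusion and the minimum SFU length. Total time at risk falls by about 5% for one child and 11 to 12% for two under the assumptions shown, and the illustrative rate shifts well within its interval. With descriptive analyses and so few patients, the main loss is the individual post-treatment course, not precision. For hepatitis the finding is one of contradictory wording, with no loss of follow-up. The point merits correction but does not threaten the PK and PD objectives.

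**What to change.** Reconcile 4.6.2, the cross-reference in 4.3.2 and the wording of 4.5.19.4 with 3.1.1.4, 3.4.6 and 4.6.1. Add one statement: removal for safety or efficacy reasons does not by itself end SFU data collection, or time at risk under 6.6, while consent and assent stand. The SFU visits or telephone interviews already in Appendix 1, Table 3 can carry this. Sections 4.5.19.4 and 4.6.1 should describe the hepatitis case consistently, so that it is recorded in one way.

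Which events stop treatment, and the best-interest ground, stay with the sponsor and the investigator. Patients who withdraw consent or assent remain outside follow-up, as 4.6.2 already says.

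The cost is a few sentences in a protocol amendment, with the ethics and regulatory approval that 9.6 requires, possibly re-consent under 8.2, and some extra site effort to retain these patients.
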